GAPDH	5'-GAA GGT GAA GGT CGG AGT C-3'	5'-GAA GAT GGT GAT GGG ATT TC-3'
PNX-14	5'-CGG CTT CAT CTC CCT GAT CG -3'	5'ACA GCC CTC TCA TTT CCT GC-3'

GAPDH (glyceraldehyde-3-phosphate dehydrogenase; PNX-14: Phoenixin14

ELISA Protocol

Serum levels of Phoenixin-14 and cytokines were measured using commercially available ELISA kits (BT Lab, Shanghai, China) according to the manufacturer's instructions.

End points

Primary endpoint: the relationship between PNX14 levels and in-hospital mortality in patients with sepsis or septic shock. Secondary endpoints: to evaluate the tendency of PNX-14 levels to be suppressed at the molecular level in patients with sepsis and their potential as a translational biomarker. Additionally, to assess the relationship between PNX14 and SOFA scores, APACHE II scores, septic shock, requirements for mechanical ventilation or renal replacement therapy, and ICU length of stay in patients with sepsis. The correlation between PNX14 levels and those of CRP, procalcitonin, IL-1 β , IL-6, IL-10, and TNF- α was also examined as part of the endpoints.

Statistical Analysis

Before the study, calculations were conducted using G*Power 3.1 with 80% power, $\alpha = 0.05$, and an expected medium effect size ($d = 0.5$), indicating that at least 64 patients were needed. This requirement was met by including 77 patients in the study.

The data were analyzed using IBM SPSS Statistics for macOS, version 29.0 (IBM Corp., Armonk, NY, USA). Descriptive statistics for continuous variables are presented as mean \pm standard deviation for normally distributed data and median (Q1–Q3) for non-normal data; categorical variables are shown as frequency (percentage). Group comparisons between developing and non-developing patients were conducted with the independent samples t-test for normally distributed continuous data and the Mann–Whitney U test for non-normal data. Normality of continuous variables was checked with the Kolmogorov–Smirnov test. For categorical variables, either the Pearson chi-square test or Fisher's exact test was used, as appropriate.

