The relative quantification (RQ, $2^{-\Delta\Delta Ct}$) values from qPCR experiments were compared between two groups (Dead and Survived). The distribution of both groups was assessed using the Shapiro–Wilk test prior to analysis, and the assumption of normality was not rejected (D group $p=0.12$; S group $p=0.17$). Homogeneity of variances was evaluated with the Levene test, which indicated unequal variances ($p=0.018$). Therefore, the differences between groups were analyzed using the Welch independent samples t-test. Additionally, the nonparametric Mann–Whitney U test was performed to verify robustness.

The ability of each biomarker to predict mortality was evaluated using ROC (receiver operating characteristic) curve analysis. The area under the curve (AUC), 95% confidence interval, optimal cut-off value, sensitivity, specificity, Youden index, and p-values were calculated. Since PNX-14 levels were inversely related to mortality in the ROC analysis, the analysis was performed with the reversed direction. Comparison of ROC curves for PNX-14 versus procalcitonin and CRP was conducted using the DeLong test.

To identify variables linked to mortality, univariate logistic regression analysis was conducted. Variables that proved significant were included in the multivariate logistic regression model to determine independent risk factors. The Backward-Wald method was employed for variable selection. Multicollinearity among independent variables was evaluated using the variance inflation factor (VIF) and tolerance values; VIF less than 5 and tolerance values between 0.40 and 0.80 were considered acceptable. The relationships between PNX, inflammatory biomarkers, and clinical severity scores were analyzed using Pearson or Spearman correlation tests, depending on the distribution of the variables, with correlation coefficients (r) and p-values reported. In all analyses, a p-value less than 0.05 was regarded as statistically significant.

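### Variables selected from an unlisted candidate set at an unadjusted 0.05 are called independent risk factors for death, although PNX-14 is the only mortality question the plan poses

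*Combined protocol and SAP*

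**What the plan says.** The End points section poses one question about death: "Primary endpoint: the relationship between PNX14 levels and in-hospital mortality in patients with sepsis or septic shock". The secondary endpoints relate PNX-14 to severity scores, shock, organ support, length of stay and inflammatory markers. None asks whether another variable predicts death.

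The Statistical Analysis section goes further. It fits univariate logistic regressions on mortality and continues: "Variables that proved significant were included in the multivariate logistic regression model to determine independent risk factors". Backward-Wald is named as the selection method, without a removal threshold. Markers are also assessed singly: "The ability of each biomarker to predict mortality was evaluated using ROC (receiver operating characteristic) curve analysis", with a p-value among the reported results. One threshold covers everything: "In all analyses, a p-value less than 0.05 was regarded as statistically significant". On sample size the section says: "This requirement was met by including 77 patients in the study".

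The section does not say which or how many variables were screened. It gives no fixed covariate set, no multiplicity rule, no internal validation and no exploratory label for this part of the analysis.

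**The concern.** One set of 77 patients chooses the variables, removes some of them, and supplies the p-values for those that remain. The result carries a label that readers take as a finding about each variable. With many candidates, some will pass by chance, and nothing in the plan tells the reader to treat a retained variable other than PNX-14 as provisional.

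Two issues need to be kept apart:

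- **Multiplicity.** The chance that at least one null variable is named grows with the number of candidates, and that number is not stated.
- **Inference after selection.** The final model's standard errors, p-values and intervals are computed as if its variables had been fixed in advance.

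At stake are the statements about variables other than PNX-14. There is also a side effect on the primary question: nothing guarantees that PNX-14 itself stays in the model.

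**Working it through.** **The plan's own figure.** It states no false-positive rate for this procedure, so there is none to reproduce. The sample-size calculation (d = 0.5, 80% power) does not address the regression.

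**Inputs from the documents.** 77 patients; p < 0.05 for entry and for declaration. The section on collection of blood samples and data names 13 admission items (age, gender, BMI, comorbidities, infection focus, blood count, CRP, procalcitonin, APACHE II, SOFA, vasopressor, ventilation, renal replacement). With four cytokines, that makes 13 + 4 = 17 besides PNX-14. The list is introduced as examples, and some items hold several variables.

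**Assumed, because the documents do not say.** 31 deaths; 3 true predictors, each shifted by 0.7 SD; removal at p > 0.10; 6 to 17 null candidates; correlation of 0 to 0.5 among them.

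**Step 1: the screen alone.** For k independent null candidates, the chance that at least one passes is 1 − 0.95^k. This gives 14.3% for k = 3, 26.5% for k = 6 and 58.2% for k = 17.

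**Step 2: the full procedure, simulated.** Univariate screen at 0.05, backward Wald elimination, then a count of datasets in which at least one null variable has p < 0.05 in the final model (800 datasets per cell):

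| Null candidates | Correlation 0 | 0.3 | 0.5 | Screen alone (independent) |
|---|---|---|---|---|
| 6 | 13.0% | 10.5% | 11.1% | 26.5% |
| 8 | 17.8% | 17.6% | 12.6% | 33.7% |
| 12 | 27.6% | 21.8% | 18.4% | 46.0% |
| 17 | 32.1% | 27.3% | 22.3% | 58.2% |

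The Monte Carlo standard error is about 1 to 2 points; for example, √(0.32 × 0.68 / 800) = 1.6 points. Repeat runs gave 11–14% for 6 null candidates, 21–33% for 17 and about 6–8% for 3. With 20 or 38 deaths in place of 31, the range for 6 to 17 was 10–33%.

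**Step 3: rate per null variable.** For independent nulls, a family rate F implies 1 − (1 − F)^(1/k) for each:

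- k = 6: 1 − 0.870^(1/6) = 2.3%
- k = 17: 1 − 0.679^(1/17) = 2.3%

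Across the simulations it was about 1–3%, below the nominal 5%. The excess comes from the number of candidates, not from a high error rate for any one of them.

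**Step 4: other assumptions.** With true predictors at log odds ratios of 0.8 to 1.0 per SD, mortality of 20–50%, removal at 0.05 or 0.10, and 1,500 runs per scenario:

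| Scenario | At least one false risk factor |
|---|---|
| 3 nulls correlated with 3 true predictors | 5–7% |
| 10 independent nulls, 3 true predictors | 24–26% |
| 20 independent nulls, PNX-14 the only true predictor | 41–44% |
| 20 independent nulls, no true predictor | 56–60% |

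**Step 5: loss of a true predictor.** Under the Step 2 assumptions, a given true predictor was absent from the final model in about 21–25% of runs, having failed the screen or been removed. The plan does not exempt PNX-14 from either step.

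**Step 6: ROC tests.** If the markers tested besides PNX-14 are CRP, procalcitonin and the four cytokines, and none is prognostic, six tests at 0.05 give 1 − 0.95^6 = 26.5% when independent, 20.7% at correlation 0.5 and 16.5% at 0.7.

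**The case against.** The plan sets 0.05 for each analysis and never promises control across a family. It is a single-centre observational cohort with one primary question, and the affected statements concern other variables. The selection step also lowers the family error: with 17 independent nulls, the screen alone gives 58% and the whole procedure 32%, while fitting all variables without selection gives about 68%. For the ROC part, the plan already reports the AUC with its 95% interval, and it does not define which biomarkers are meant.

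Much of this stands, and it rules out three stronger readings.

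- **That every recorded variable is tested against death.** The data-collection section lists what was recorded; the analysis section does not say what was screened. Seventeen is a count of named items, not of tests. Treating all 17 as null is also a high-end case, because the list includes severity scores.
- **That 11–33% is a property of the plan.** It depends on assumed deaths, true predictors, null candidates, correlation and removal threshold.
- **That the second test fails.** A null variable that has passed the screen is declared significant 28–56% of the time, but that is conditional on an association already found by chance. It is not comparable with an unconditional 5%.

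What the objection does not answer is the label. A plan with no family control can still describe such results as exploratory. This one presents them as determined risk factors.

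**Conclusion.** The point holds in this form: an unlisted set of candidates, selection at an unadjusted 0.05, and a conclusive label for whatever survives, on a question that the endpoints ask only of PNX-14.

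The size is conditional. Under the base assumptions (31 deaths, 3 true predictors, removal at p > 0.10), the chance of at least one false risk factor is about 11–33% for 6 to 17 null candidates and about 6–8% for 3. It rises with more null candidates or fewer true predictors. The distortion of p-values and intervals after selection is real, but it is not quantified here.

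A reader might infer that the primary conclusion on PNX-14 is invalid. None of these error rates concerns PNX-14, so the documents do not support that. The link to the primary question is narrower: the planned selection can drop PNX-14 from the multivariable model. This should be corrected, but it does not overturn the study.

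**What to change.** In the Statistical Analysis section:

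1. Replace the stated aim of determining independent risk factors. Say that the PNX-14 coefficient is the only inferential target of the multivariable model, and that PNX-14 is kept in it whatever the screen or the Backward-Wald step shows.
2. Present the other coefficients as adjustment terms. Describe any other selected predictor as hypothesis-generating, not as an independent risk factor.
3. Label ROC results for markers other than PNX-14 as descriptive, giving the AUC with its 95% interval.

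Listing the candidates screened and the removal threshold would also let a reader judge the multiplicity. Because the section already reports 77 included patients and some results, the report should say that these changes were made after data collection.

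The cost is wording in the plan and the report, plus a refit if PNX-14 was dropped; no new patients or measurements are needed. The downside is that the study can no longer claim other variables as independent risk factors. One limit remains: if the adjustment terms are still chosen from the data, the PNX-14 interval still ignores that choice.

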**Suppression of Phoenixin-14 Predicts Mortality in Sepsis: Evidence from
Serum Levels and Gene Expression**

[name] [name]

30.04.2025

Department of Anesthesiology and Reanimation, Firat University Medicine Faculty Hospital,
Elazig 23300, Turkey

Study Protocol

Study Design and Patients

In this prospective observational cohort study, patients aged 18 years and older admitted to our tertiary intensive care unit with diagnoses of sepsis and/or septic shock were evaluated. Ethical approval was obtained from the Firat University Non-Interventional Research Ethics Committee on March 27, 2024, with the number 23376. The entire study was funded by the Firat University Scientific Research Projects Coordination Unit (FUBAP), under project number TF.24.11. Our study adhered to the Helsinki Declaration and the Strengthening the Reporting of Observational Studies in Epidemiology (STROBE) guidelines.

The treatment protocol for patients was followed according to the Sepsis-3 guidelines (1), and antibiotic therapy was administered in consultation with an infectious disease specialist, aiming at the source of sepsis. Septic shock was also defined according to the Sepsis-3 guidelines (1), based on the requirement for vasopressor support to maintain adequate mean arterial pressure despite adequate fluid resuscitation.

Patients under the age of 18, patients who were discharged/transferred or died within 72 hours after being diagnosed with sepsis, patients/relatives who refused to participate in the study, pregnant women, patients using chronic steroids, patients whose blood samples were collected

under inappropriate conditions, and patients with a history of malignancy or immunosuppression were also excluded from the study.

The study was started with participants who agreed after signing an informed consent form.

Collection of Blood Samples and Data

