At the time of ICU admission, parameters such as age, gender, body mass index (BMI), comorbidities, infection focus, complete blood count, CRP, procalcitonin, Acute Physiology and Chronic Health Evaluation (APACHE) II score, Sequential Organ Failure Assessment (SOFA) score, vasopressor requirement, mechanical ventilation need, and renal replacement therapy requirement were recorded. On the first day of hospitalization, 3 mL of blood was routinely collected from patients for biochemical analysis. The levels of IL-6, TNF- α , IL-1 β , IL-10, and PNX14 were measured using real-time PCR, while serum levels were determined using ELISA. Blood samples were collected once at ICU admission to assess baseline PNX-14 levels for early prognostic evaluation.

RNA Isolation

Total RNA was isolated from peripheral blood samples using the NucleoSpin RNA Blood kit (Macherey-Nagel, Germany) according to the manufacturer's instructions. RNA concentration and purity were assessed using a Qubit 2.0 Fluorometer (Thermo Fisher Scientific).

RNA Quality Control – Agarose Gel Electrophoresis

RNA integrity was assessed by agarose gel electrophoresis. Briefly, RNA samples were separated on a 1% agarose gel and visualized using a gel documentation system to confirm RNA integrity, according to standard laboratory procedures.

RNA Concentration Measurement – Qubit Fluorometric Method

RNA concentration and quality were assessed using a Qubit 2.0 Fluorometer (Thermo Fisher Scientific, USA) and the Qubit RNA HS Assay Kit, following the manufacturer's recommended protocol.

cDNA Synthesis

Complementary DNA (cDNA) was synthesized from total RNA using the High-Capacity cDNA Reverse Transcription Kit (Thermo Fisher Scientific, USA) as per the manufacturer's protocol.

Quantitative Real-Time PCR (qRT-PCR)

Quantitative real-time PCR analysis was performed using SYBR Green Master Mix (AMPLIFYME SYBR Universal Mix) on an Applied Biosystems StepOnePlus system. GAPDH was used as the reference gene due to its reported expression stability in peripheral blood samples under inflammatory conditions. Relative gene expression was calculated using the $2^{-\Delta\Delta Ct}$ method, with GAPDH as the internal control. In the absence of a healthy control group, the survivor group was used as the calibrator for relative expression analysis. Primer sequences are listed in Table 1.

Table 1. Primers used in the study

	Forward Primer	Reverse Primer

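### PNX-14 reaches the final multivariable model only by surviving screening and Backward-Wald, with no severity score forced in; separately, cut-off accuracy is scored in the cohort that chose the cut-off

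*Combined protocol and SAP*

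**What the plan says.** The last paragraph of Statistical Analysis runs univariate logistic regressions for mortality and then states: "Variables that proved significant were included in the multivariate logistic regression model to determine independent risk factors". The next sentence gives the removal step: "The Backward-Wald method was employed for variable selection". No exception is made for PNX-14, SOFA or APACHE II, and no removal level is given.

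The severity information exists at admission. Under Collection of Blood Samples and Data, both scores are recorded, and "vasopressor requirement, mechanical ventilation need, and renal replacement therapy requirement were recorded". The only stated analysis that pairs the scores with PNX-14 is correlation; they can enter the regression only through the same screen. That section also describes PNX-14 by PCR, "while serum levels were determined using ELISA", and the regression paragraph does not say which measure is entered.

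For the ROC analysis, the AUC with its confidence interval, "optimal cut-off value, sensitivity, specificity, Youden index, and p-values were calculated". Only one cohort is described (77 patients), and no split sample, cross-validation, bootstrap or external cohort is mentioned.

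**The concern.** The title reads "Suppression of Phoenixin-14 Predicts Mortality in Sepsis", a secondary endpoint concerns "their potential as a translational biomarker", and the regression is meant to identify independent risk factors. For that purpose a reader wants the PNX-14 OR beside a severity score, whatever its p-value. The plan does not guarantee this, for three reasons.

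- PNX-14 may drop out, leaving no final-model OR. Whether the starting-model OR would then be shown is not stated.
- When PNX-14 stays, its OR is reported because it survived, and is then on average too far from 1.
- The final model may contain neither SOFA nor APACHE II.

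The cut-off raises a separate issue. Sensitivity, specificity and the Youden index at a threshold chosen to look best in these patients are apparent values, and are expected to be lower in new patients.

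**Working it through.** **Inputs from the documents.** 77 patients; significance at 0.05; univariate screen, then Backward-Wald with nothing forced in. The documents give no OR, AUC, death count or removal level, so there is no plan figure to reproduce here and every frequency below is illustrative.

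**Assumptions.** 40% deaths (0.40 × 77 ≈ 31 deaths, 46 survivors); 20 candidates, 13 of them noise; removal at p > 0.10; SOFA OR 1.5-2.5 and APACHE II OR 1.0-1.5 per SD; age OR 1.3 per SD; three organ-support variables with OR 1 or 2 each. Correlations: PNX-14 with SOFA -0.4 and with APACHE II -0.3; SOFA with APACHE II 0.6; organ support (latent scale) -0.3, 0.5 and 0.4 with PNX-14, SOFA and APACHE II. There were 1,000 cohorts per setting. The fixed model is PNX-14 + SOFA + age.

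**Step 1: the selection rule.**

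| True PNX-14 OR | Absent from final model | No adjusted OR at any step* | Median OR when kept | Fixed model, always reported | Fixed model, p < 0.05 only |
|---|---|---|---|---|---|
| 0.74 | 64-75% | 15-59% | 0.42-0.51 | 0.65-0.74 | 0.41-0.48 |
| 0.61 | 44-53% | 7-31% | 0.38-0.47 | 0.53-0.60 | 0.39-0.46 |
| 0.40 | 7-17% | 0-3% | 0.30-0.35 | 0.35-0.39 | 0.31-0.35 |
| 0.30 | 1-7% | under 1% | 0.23-0.27 | 0.27-0.29 | 0.25-0.28 |

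*PNX-14 fails the screen; from smaller runs over some of the settings, in which absence from the final model reached 58% at true OR 0.61.

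On the log scale at true OR 0.61, ln 0.61 = -0.494. The kept estimates are ln 0.47 = -0.755 to ln 0.38 = -0.968, or 1.5 to 2.0 times the truth. The fixed model gives -0.511 to -0.635, or 1.0 to 1.3 times. At true OR 0.30 (ln = -1.204), the kept estimates are 1.1 to 1.2 times the truth. The last column shows the cause: restricting even the fixed model to significant runs reproduces most of the excess. It comes mainly from selective reporting, not from the stepwise search.

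A separate simulation with 9 candidates, 30% or 50% deaths, removal at 0.05 or 0.10 and PNX-14 coded as OR 1.65 (1/1.65 = 0.61) agrees. PNX-14 passed the screen in 70-91% of datasets and stayed in the final model in 43-57%. The median OR was 2.07-2.66 when kept, against 1.71-1.82 from a fixed PNX-14 + SOFA model.

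**Step 2: models with neither score.** Among samples with a significant final PNX-14 term (true OR 0.40-0.74), neither score remained in 4-79%, depending mainly on the assumed SOFA and APACHE II effects. In 48-100% of those samples a score had been in the starting model, and in 62-100% the fixed model was also significant. Median ORs there were 0.25-0.48 (final) and 0.28-0.53 (fixed). No severity variable of any kind remained in 1-65% of PNX-14-significant samples if organ support has no effect of its own, and in 0-11% if each such variable has OR 2.

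**Step 3: no PNX-14 effect.** A significant final PNX-14 term appeared in 2-6% of samples, about nominal.

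**Step 4: the cut-off.** Binormal samples, 31 deaths and 46 survivors, 4,000 per setting. Optimism = apparent minus true Youden index at the chosen cut-off.

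| AUC | Apparent | True | Optimism |
|---|---|---|---|
| 0.50 | 0.14 | 0 | 0.14 |
| 0.60 | 0.25 | 0.12 | 0.13 |
| 0.70 | 0.38 | 0.27 | 0.11 |
| 0.80 | 0.52 | 0.43 | 0.09 |
| 0.90 | 0.69 | 0.61 | 0.08 |

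With 23 to 38 deaths the range is 0.08-0.15. At AUC 0.80, sensitivity is 0.76 apparent against 0.70 true, and specificity 0.76 against 0.73.

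**The case against.** The strongest reply is that much of this is a reporting gap. A PNX-14 that passes the screen already has an adjusted OR in the starting model, and that OR is less exaggerated: median 0.54-0.58 at true OR 0.61. A reader might infer that no adjusted estimate exists unless PNX-14 survives both steps. The documents do not support that, and the third column of the selection table shows how much rarer it is. What stands is that the plan does not say the starting model will be shown.

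A reader might also infer that the final model carries no severity adjustment. The text says only that nothing is forced in: a score may be selected, organ-support variables may remain, and the fixed model often agrees.

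Next, "Primary endpoint: the relationship between PNX14 levels and in-hospital mortality in patients with sepsis or septic shock" requires no adjustment, and the title can rest on the ROC analysis. Both points are right. They limit the concern to the independence claim and to the cut-off figures.

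Finally, the frequencies rest on assumed effects and correlations, and the lack of validation is read from silence. That is also right. The argument rests on the stated rule; the simulations only show plausible size.

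**Conclusion.** The point holds as a recommended, low-cost improvement. The plan makes the final-model PNX-14 OR conditional on surviving two selection steps and assures neither severity score a place. Reporting only survivors exaggerates weak to moderate effects appreciably and strong effects little. How often an independence claim would come from a model with neither score cannot be fixed from the documents. Cut-off sensitivity, specificity and Youden index are apparent values.

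Not affected are the unadjusted group comparisons, the univariate OR, the AUC with its confidence interval and the DeLong test. A reader might infer that the procedure inflates false independence claims; the simulation with no PNX-14 effect does not show this.

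Confidence is high in the reading of the text. The sizes depend on the stated assumptions, chiefly the death rate, effect sizes, correlations and removal level.

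**What to change.** 1. Report, whatever its p-value, one fixed logistic model of in-hospital death on serum (ELISA) PNX-14 (continuous, per SD), SOFA and age, with OR and 95% CI. Swap in APACHE II for SOFA as a sensitivity analysis; which score comes first is a convention. Label the model post hoc, because Statistical Analysis already reports results (for example, a Levene p-value of 0.018). If PCR expression is also claimed to be independent, repeat the model separately with log2 RQ per SD.
2. Show the starting Backward-Wald model beside the final one. List the variables screened and the removal level, and say whether each score was screened out or entered and then removed. Label the selected model exploratory.
3. Beside the apparent cut-off figures, give bootstrap optimism-corrected sensitivity, specificity and Youden index, re-selecting the cut-off in every resample. State how the cut-off was chosen and call it exploratory.

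**Cost.** A short re-analysis of existing data and a few sentences. The adjusted CI will be wide (upper/lower ratio about 3 to 6 in simulation), and the accuracy figures will probably look less favourable. The bootstrap removes only about 60-70% of the optimism: at AUC 0.70 the Youden index goes from 0.39 to 0.31 against a true 0.27, and 0.08/0.12 = 67%. Some confounding remains: with no PNX-14 effect and OR 2 for each organ-support variable, the fixed model's large-sample OR is 0.88-0.91, with p < 0.05 in 5-7% of samples. Nothing here restores pre-specification.

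### The 0.80 ceiling on tolerance runs the wrong way: it leaves the least collinear predictors outside the range called acceptable, and the tolerance range does not correspond to the VIF limit beside it

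*Combined protocol and SAP*

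**What the plan says.** The last paragraph of the Statistical Analysis section describes the logistic regression for mortality. Candidates are first screened one at a time, and then: "Variables that proved significant were included in the multivariate logistic regression model to determine independent risk factors". On selection within that model it says: "The Backward-Wald method was employed for variable selection".

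Collinearity comes next. "Multicollinearity among independent variables was evaluated using the variance inflation factor (VIF) and tolerance values", and the criterion is "VIF less than 5 and tolerance values between 0.40 and 0.80 were considered acceptable".

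The section gives no reason for an upper bound on tolerance. It also does not say what was done with a predictor outside the stated limits.

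**The concern.** VIF and tolerance are one quantity on two scales. A criterion that uses both should give the same cut-off twice, and here it does not. In addition, high tolerance means that a predictor shares little with the others, so a collinearity rule needs a lower bound on tolerance and has no use for an upper one. The stated range has both.

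The check applies to the model meant to identify independent risk factors for death. If the range had been used to decide which variables could stay, it would have counted against the predictors with the least collinearity. A reader trying to reproduce the check also cannot tell whether the intended floor was tolerance 0.20 or 0.40.

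**Working it through.** **Inputs**, all from the Statistical Analysis section: a VIF limit ("VIF less than 5") and a tolerance range ("tolerance values between 0.40 and 0.80 were considered acceptable").

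**Identity.** For predictor j, let R² come from regressing it on the other predictors. Then tolerance = 1 − R² and VIF = 1/(1 − R²), so tolerance = 1/VIF.

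**Step 1: try to obtain one stated limit from the other.**
- VIF limit: 1/5 = 0.20, so VIF < 5 is tolerance > 0.20 (R² < 0.80), with no upper limit. The stated floor of 0.40 is not reproduced.
- Tolerance floor: 1/0.40 = 2.50, so the floor is VIF 2.50 (R² = 1 − 0.40 = 0.60).
- Tolerance ceiling: 1/0.80 = 1.25, so the ceiling is VIF 1.25 (R² = 1 − 0.80 = 0.20).

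**Step 2: apply both limits to the same predictor** (end points of the tolerance range counted as inside).

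| Tolerance | VIF | R² | VIF < 5 | Tolerance 0.40–0.80 |
|---|---|---|---|---|
| 0.15 | 6.67 | 0.85 | outside | outside |
| 0.25 | 4.00 | 0.75 | within | outside |
| 0.40 | 2.50 | 0.60 | within | within |
| 0.60 | 1.67 | 0.40 | within | within |
| 0.80 | 1.25 | 0.20 | within | within |
| 0.95 | 1.05 | 0.05 | within | outside |
| 1.00 | 1.00 | 0.00 | within | outside |

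Every value inside the tolerance range also meets the VIF limit. Read jointly, the rule is therefore determinate: it reduces to the tolerance range, and VIF < 5 never binds. The VIF limit is met and the tolerance range is not in two zones: VIF above 2.50 to below 5, and VIF 1.00 to below 1.25.

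**Step 3: what each zone means.** Collinearity inflates a standard error by √VIF (exact for linear regression, approximate for logistic).
- Above the ceiling: less than √1.25 = 1.118, so under 11.8% inflation.
- Inside the range: 1.118 to √2.50 = 1.581, so 11.8% to 58.1%.
- At the VIF limit: √5 = 2.236, so 123.6%.

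The first zone is only a looser limit beside a stricter one. The second is the error: the range takes in a predictor with about 58% inflation and leaves out one with none.

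**Illustration with two predictors**, where R² = r². At |r| = 0.30, tolerance is 1 − 0.09 = 0.91, VIF is 1/0.91 = 1.10 and inflation is √1.099 − 1 = 4.8%; this weakly correlated pair falls outside the range. The ceiling is crossed whenever |r| < √0.20 = 0.447.

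The documents give neither the number of predictors in the model nor their correlations. These figures describe the rule; they do not measure anything in this study.

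**The case against.** Four points can be made for the text as it stands.

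- **The pair of limits is not a contradiction.** This stands. The scales convert exactly, and a loose limit beside a tighter one is redundant. A reader might infer that the two limits conflict; taken together, they do not. This defence covers the 0.40 floor, which may simply be stricter. It does not cover the ceiling, because no conservative purpose is served by leaving out the absence of collinearity.
- **Nothing was excluded on this rule.** A reader might infer that weakly correlated predictors were dropped, or that the mortality model is wrong. The documents do not support either inference. They say which values were acceptable and attach no consequence to the rest. The selection steps they name are univariate significance and Backward-Wald elimination, and collinearity is not among them.
- **The range may be a result.** The section was written after the analysis and mixes findings with methods. For the qPCR data, for example, it says "Homogeneity of variances was evaluated with the Levene test, which indicated unequal variances" (p = 0.018). If 0.40 to 0.80 was what the model showed, every VIF lay between 1.25 and 2.50, all met the VIF limit, and only the wording is wrong. This is possible but not established, because the sentence is worded as a criterion. It needs correcting on either reading.
- **The inflation figures are not study results.** This stands, and they are not offered as such.

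**Conclusion.** The criterion is wrong as written, and the point is minor. The error is the 0.80 ceiling, which places predictors with VIF below 1.25, down to a fully uncorrelated one at VIF 1.0, outside the stated acceptable range. The mismatch between VIF < 5 (tolerance > 0.20) and tolerance 0.40 to 0.80 (VIF 1.25 to 2.50) is a secondary matter of redundancy.

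This rests only on the identity tolerance = 1/VIF and on reading the sentence as the criterion it says it is. Confidence is high for the wording defect. No effect on results is shown: harm to the multivariable model would require that a variable was left out because of this check, and the documents do not report that. The group comparisons, univariate regressions, ROC and DeLong analyses and correlations do not use the rule.

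**What to change.** - Delete the 0.80 upper bound.
- State one limit on matching scales: VIF < 5 (tolerance > 0.20) or, if the stricter floor was meant, VIF < 2.5 (tolerance > 0.40). The documents do not show which was intended, so the authors must say.
- If 0.40 to 0.80 was the range seen in the fitted model, move it to the results and label it as observed.
- Add what was done with any predictor outside the limit, and confirm that none was left out of the multivariable model for tolerance above 0.80.

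The cost is one or two sentences. The multivariable logistic model needs to be re-run only if a variable was left out on that ground.
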